9.4 STATISTICAL ANALYSES

9.4.1 GENERAL APPROACH

There are no categorical outcomes. Key measures are all continuous outcomes, and are described in detail in the next section. They will be analyzed according to pre- versus post-stimulation means. We will also report standard errors for each outcome. Key outcomes have multiple associated measures. Multiple measures will be used to assess reliability by parallel forms.

We will use standard frequentist cut-offs of $p < 0.05$ for all statistical tests, correcting for multiple comparisons. Key t-tests will include pre-post distinctions in E/I balance measures, working memory performance measures, and measures of criticality.

Covariates of no interest to be included are sex and age which we will incorporate via multiple regression to ask whether cTBS alters key outcomes (described in the next session).

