9.4.2 ANALYSIS OF THE PRIMARY ENDPOINT(S)

The following key outcomes will be assessed in this study. All measures are interval with the exception of the categorical covariate of sex.

- Subjective effort
 - Likert scale ratings (ranging from 1-10) of task-induced effort, demand, time pressure, and stress
 - subjective values as estimated from an indifference point discounting procedure
 - self-reported motivation to engage in demanding tasks on a set of Likert scales with continuous values ranging from 0-20
- E/I balance
 - fEI derived measure with exponents ranging approximately from 0.0-2.0
 - power-law exponents with exponents approximating -2.0
- Critical dynamics
 - Long range temporal correlations – a derived measure with exponents ranging approximately from 0.5-1.0
 - Avalanche size and duration distribution exponents approximating -2.0 and -1.5, respectively
- N-back working memory performance
 - overall accuracy rate as a percentage
 - median correct reaction times by trial type: lures versus targets versus regular trials
 - the discrimination index d'

Primary analyses of these outcomes will entail multiple regression models in which outcomes will be regressed on cTBS condition (target versus sham), controlling for sex and age.

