9.4.3 ANALYSIS OF THE SECONDARY ENDPOINT(S)

Secondary endpoints will be inter-correlations among the primary endpoint measures. Namely, these correlations will test whether the degree to which cTBS alters one measure correlates with stimulation effects on other measures. Given the large number of possible correlations, we will only test for correlations among those measures which show a reliable stimulation effect in the first place. We will then correct for multiple comparisons among these correlations by the false discovery rate method to control for Type I errors, limiting them to no more than 5% chance.

We will use Pearson's correlations for all tests since our outcome measures are continuous, interval measures.

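### Section 9.4.1 assesses reliability by parallel forms, but the measures in 9.4.2 are not parallel forms, so their intercorrelation does not estimate reliability

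*Protocol*

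**What the plan says.** Protocol section 9.4.1 (General Approach) states "Key outcomes have multiple associated measures" and then "Multiple measures will be used to assess reliability by parallel forms". The measures are listed by outcome in section 9.4.2:

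- **N-back:** "overall accuracy rate as a percentage", then reaction times given as "median correct reaction times by trial type: lures versus targets versus regular trials", and lastly "the discrimination index d"-prime.
- **Subjective effort:** a first set given as "Likert scale ratings (ranging from 1-10) of task-induced effort, demand, time pressure, and stress"; next to these, discounting results given as "subjective values as estimated from an indifference point discounting procedure"; and motivation scales running from 0 to 20.
- **E/I balance:** a functional E/I measure of about 0 to 2, and power-law exponents near -2.
- **Critical dynamics:** long-range temporal correlation exponents of about 0.5 to 1.0, and avalanche size and duration exponents near -2.0 and -1.5.

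No measure is described as an alternate version of another, and no split-half or retest coefficient is named. Section 9.4.3 makes correlations between stimulation effects the secondary endpoints: "these correlations will test whether the degree to which cTBS alters one measure correlates with stimulation effects on other measures". Section 9 says that no formal SAP will be written, so the sentence in 9.4.1 is the stated method.

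**The concern.** Two forms are parallel when they measure the same true score with equal and independent error. Only then does their correlation equal the reliability of either one. The lists in 9.4.2 break this in two ways.

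- **Shared responses.** Accuracy and d-prime are two summaries of the same hits and false alarms. Chance variation in the responses moves both together and looks like agreement.
- **Different constructs.** Effort ratings, discounting values and motivation are not the same true score, and neither are accuracy and reaction time. Their correlation mixes reliability with how closely the constructs are related.

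The coefficient could therefore certify a noisy measure or condemn a sound one. This matters most for 9.4.3. A null correlation between two stimulation effects may mean that no relation exists or that the effect scores are too noisy to show it. A valid reliability estimate helps to separate the two, and the stated method does not supply one.

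**Working it through.** The protocol states no reliability figure, so there is nothing to reproduce. The check asks what the stated method returns when the true reliability is known.

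**Inputs.** The measures are those in 9.4.2 and n = 30 is from 9.2. Trial counts and response rates are not in the protocol. Assumed: 20 to 60 targets, 40 to 140 non-targets, hit rate 0.70 to 0.90, false-alarm rate 0.05 to 0.20, and both scores computed over the same trials.

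**1. Same responses, zero true reliability.** Every simulated participant has the same true hit rate h and false-alarm rate f, so all differences between participants are noise. With nT targets and nN non-targets:

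- accuracy = (H + nN - F)/(nT + nN), with H hits and F false alarms, both binomial;
- d-prime = z[(H + 0.5)/(nT + 1)] - z[(F + 0.5)/(nN + 1)].

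A first-order approximation can be done by hand. Let vH = nT·h(1-h) and vF = nN·f(1-f). Let bH = 1/[nT·φ(z_h)] and bF = 1/[nN·φ(z_f)], where φ is the normal density. Then

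r ≈ (vH·bH + vF·bF) / √[(vH + vF)(vH·bH² + vF·bF²)].

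- *30 targets, 70 non-targets, h = 0.80, f = 0.10.* vH = 4.8, vF = 6.3, φ = 0.280 and 0.1755, bH = 0.1191, bF = 0.0814. The numerator is 1.084, and r ≈ 1.084/√(11.1 × 0.1098) = 0.98.
- *20 targets, 80 non-targets, h = 0.85, f = 0.15.* vH = 2.55, vF = 10.2, φ = 0.2332 for both, bH = 0.2144, bF = 0.0536. The numerator is 1.094, and r ≈ 1.094/√(12.75 × 0.1466) = 0.80.

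Simulation (30 participants, 1,500 replicates per scenario) gave 0.97 and 0.78 for these two cases. Over all 20 assumed scenarios the mean correlation ran from 0.78 to 0.99, and it was at least 0.88 in 18 of them. Two independent administrations of the same zero-reliability task gave -0.01 to 0.01.

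**2. Same responses, real differences added.** With a between-person SD of 0.5 in d-prime (30/70 trials, h = 0.80, f = 0.10), the same-responses correlation stays at 0.97. The true retest correlation is 0.71 for accuracy and 0.67 for d-prime. The coefficient is the same whether reliability is zero or about 0.7, so it does not track reliability.

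**3. Different constructs, independent errors.** The expected correlation is the construct correlation times √(rel1 × rel2). With equal reliabilities this is construct correlation × reliability.

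| Assumed construct correlation | Reliability 0.7 | Reliability 0.9 |
|---|---|---|
| 0 | 0 | 0 |
| 0.2 | 0.14 | 0.18 |
| 0.3 | 0.21 | 0.27 |
| 0.5 | 0.35 | 0.45 |

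Here measures with reliability 0.7 to 0.9 would be reported at 0 to 0.45.

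**4. Check on a possible EEG remedy.** Splitting one recording into interleaved odd and even segments is unsafe for the long-range correlation exponent, because neighbouring segments are dependent. In simulated 5-minute series (assumed 10 Hz envelope, true exponent 0.8, segments of 1 to 5 s, 100 runs per setting) with no true differences between participants, the odd and even exponents still correlated 0.28 to 0.54. A separate run gave about 0.42 for interleaved segments and about -0.1 for contiguous halves.

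**The case against.** The strongest reply is that the sentence carries little weight. The coefficient is not an endpoint, a hypothesis, a term in the 9.4.2 regressions or a threshold. The rule in 9.4.3 that only measures with a reliable stimulation effect go forward is most naturally read as meaning a statistically significant effect, not a reliability coefficient. This stands, and it limits the point to minor.

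Four stronger readings are tempting, and the documents do not support them.

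- **That reliability would look high throughout.** Inflation is shown only for accuracy and d-prime. It is plausible for avalanche size and duration exponents, which describe the same avalanches, but nothing in the protocol lets one size it. For different constructs the error runs low.
- **That accuracy and d-prime share all their error.** Correlations of 0.78 to 0.99 show that most of it is shared, but in general not all.
- **That the 9.4.3 correlations are underpowered because of this sentence.** Attenuation of difference scores is a real limit at n = 30. Sizing it needs per-session reliabilities, between-session correlations and a true correlation, none of which the protocol gives. Correcting the sentence would leave that power unchanged.
- **That the primary comparisons are compromised.** They do not use the coefficient.

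The reply does not rescue the method itself. 9.4.1 names a specific analysis, and applied to the 9.4.2 measures it does not estimate what it claims to.

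**Conclusion.** The point holds as a minor one. Section 9.4.1 fixes a reliability method that the measures in 9.4.2 cannot satisfy. Under the assumed trial counts and response rates, the accuracy and d-prime pair would show about 0.8 to 0.99 with zero true reliability. Under assumed construct correlations of 0 to 0.5, measures of different constructs with reliability 0.7 to 0.9 would show 0 to 0.45. The exact values rest on those assumptions. The conclusion that the coefficient does not estimate reliability follows from the definitions and does not depend on them. The consequences are confined to any reliability statement the trial makes and to how null correlations in 9.4.3 are read.

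**What to change.** Replace the parallel-forms sentence in 9.4.1 with the following plan.

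- Report correlations between the measures of one outcome as convergent validity only.
- For N-back accuracy, d-prime and reaction time, estimate reliability by odd/even-trial split halves with the Spearman-Brown correction.
- For the EEG measures, report an intraclass correlation between the pre-stimulation rest recordings of the two sessions. Section 9.1 already uses pre-stimulation rest as a comparator, and section 8.1 records EEG throughout the stimulation session. Do not use interleaved segments of one recording.
- For ratings, motivation scales and indifference-point values, claim no split-half coefficient unless the task supplies repeated items; the protocol does not show that it does.
- Where the data allow, report beside each 9.4.3 correlation the reliability of the effect score actually used. Section 9.1 defines the E/I and criticality effects as change from pre-stimulation rest and the effort effect as dlPFC versus angular gyrus, so one difference score does not serve for all.

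The cost is one sentence and a small extra analysis of data already planned. No new participants, visits or procedures are needed.

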9.4.2 ANALYSIS OF THE PRIMARY ENDPOINT(S)

The following key outcomes will be assessed in this study. All measures are interval with the exception of the categorical covariate of sex.

- Subjective effort
 - Likert scale ratings (ranging from 1-10) of task-induced effort, demand, time pressure, and stress
 - subjective values as estimated from an indifference point discounting procedure
 - self-reported motivation to engage in demanding tasks on a set of Likert scales with continuous values ranging from 0-20
- E/I balance
 - fEI derived measure with exponents ranging approximately from 0.0-2.0
 - power-law exponents with exponents approximating -2.0
- Critical dynamics
 - Long range temporal correlations – a derived measure with exponents ranging approximately from 0.5-1.0
 - Avalanche size and duration distribution exponents approximating -2.0 and -1.5, respectively
- N-back working memory performance
 - overall accuracy rate as a percentage
 - median correct reaction times by trial type: lures versus targets versus regular trials
 - the discrimination index d'

Primary analyses of these outcomes will entail multiple regression models in which outcomes will be regressed on cTBS condition (target versus sham), controlling for sex and age.

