3 OBJECTIVES AND ENDPOINTS

OBJECTIVES	ENDPOINTS	JUSTIFICATION FOR ENDPOINTS	PUTATIVE MECHANISMS OF ACTION
Primary			
Test whether continuous theta-bursts stimulation induces sub-critical dynamics in the cortex	Diminished markers of critical dynamics include reduced long-range temporal correlations measured by detrended fluctuation analysis, and sub-critical avalanche branching ratios.	Long-range temporal correlations and avalanche branching dynamics are widely used metrics of distance from the critical point (degree of sub-criticality) in EEG studies.	Long-range temporal correlations and avalanche branching ratios of 1.0 are emergent properties of dynamical systems at a critical point. By reducing the E/I balance, continuous theta burst stimulation should make the brain more sub-critical, thus dampening these emergent properties.
Test whether continuous theta-bursts stimulation to dlPFC diminishes working memory function relative to stimulation to the angular gyrus.	Lower discrimination (d') accuracy and slower reaction times on the N-back following dlPFC stimulation.	Criticality affords dynamic flexibility as needed for rapid, reliable updating in the N-back task, and also flexible task switching. Prior work has shown that dlPFC continuous theta burst can undermine working memory function. Here we test the specific hypothesis that this reflects the effects	A decrease in the E/I balance in the dlPFC produced by dlPFC theta-burst stimulation should make the brain more sub-critical, thus impairing functional flexibility afforded by a critical state. This should matter most

OBJECTIVES	ENDPOINTS	JUSTIFICATION FOR ENDPOINTS	PUTATIVE MECHANISMS OF ACTION
		of TMS-induced sub-criticality in the dlPFC.	in the dlPFC which is a key nexus of higher-order working memory function.
Test whether continuous theta burst stimulation to the dlPFC increases subjective cognitive effort relative to stimulation to the angular gyrus.	Steeper discounting of rewards contingent on the expenditure of cognitive effort following dlPFC stimulation versus angular gyrus stimulation.	By virtue of dlPFC's involvement in working memory and cognitive control, it is hypothesized to play a key role in subjective cognitive effort. We specifically predict that critical dynamics in the dlPFC are what the brain tracks as subjective effort.	
Secondary			

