9.2 SAMPLE SIZE DETERMINATION

While studies on the effects of continuous theta-burst stimulation (cTBS) on critical dynamics have never been conducted, power calculations are based on prior work showing that cTBS can alter E/I balance and working memory function. Specifically, Schicktanz et al. (2015) found that a single train of cTBS to the left dorsolateral prefrontal cortex reduced N-back task accuracy (the same working memory task we will use in the present study) with an effect size on accuracy of $d = 1.39$, 3–21 minutes post-stimulation. This performance effect was established for the 2-back which is our mid-difficulty level. Using g*Power (Faul et al., 2007), we estimate that if the true effect size remains the same, we will have a 95% chance of detecting a cTBS effect on 2-back performance with 30 participants at $p < 0.05$. Importantly, with 30 participants, we will still have 80% power to detect a group difference in performance even if the true

effect size is less than half as large ($d = 0.53$). As such, our target recruitment is set at 30 participants (but will run additional to reach 30 complete participant-session sets, as needed, due to drop-out).

While effect sizes can vary in cTBS owing to considerable inter-individual differences in response to stimulation, we are taking additional measures to reduce reliability including participant-specific brain images and neuronavigation, and also the use of two, rather than one train of cTBS. As such, if anything, we expect the prior estimates to be a lower bound on what we observe.

While this estimate is based on working memory performance alone, this outcome is arguably the most important because it is the one measure that has been linked with E/I balance, with subjective effort, and with critical dynamics in other studies. As such, this measure was selected because it is also informative about all primary and secondary outcomes.

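### Section 3 defines impaired working memory as lower d' and slower reaction times, but 9.4.2 tests three kinds of N-back measure (up to five) with none named as deciding, and the 80% power in 9.2 holds for only one uncorrected test

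*Protocol*

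**What the plan says.** - Section 3 (Objectives and Endpoints), working-memory row: the endpoint is "Lower discrimination (d') accuracy and slower reaction times on the N-back following dlPFC stimulation". The two parts are joined by a plain conjunction. Percent accuracy is not mentioned. The session-order row of the same table uses d' as the gloss for accuracy.
- Section 9.4.2, N-back performance, has three bullets: "overall accuracy rate as a percentage"; "median correct reaction times by trial type: lures versus targets versus regular trials"; and the discrimination index d'. The primary analysis regresses each listed outcome on stimulation condition, with sex and age as covariates. The section sets no order among the measures and names no load level.
- Section 9.2 cites a study in which one train of cTBS "reduced N-back task accuracy (the same working memory task we will use in the present study) with an effect size on accuracy of" d = 1.39, and adds: "This performance effect was established for the 2-back which is our mid-difficulty level". It goes on that "with 30 participants, we will still have 80% power to detect a group difference in performance even if the true" effect is d = 0.53. It calls working-memory performance the most important outcome, but that is a domain and not a measure.
- Section 9.4.1 sets p < 0.05 with correction for multiple comparisons. It names no method or family for the primary tests, and says that multiple measures serve to assess reliability.
- Section 9.1 states no working-memory hypothesis. The synopsis endpoint is simply working memory performance. The opening of Section 9 says there will be no formal SAP.

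**The concern.** The two sections give different accounts of what would show the objective met. On a strict reading of Section 3, d' must fall and reaction time must lengthen. Section 9.4.2 has no such conjunction, adds a measure that Section 3 does not contain, and splits reaction time by trial type without saying which type counts.

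The measures are not interchangeable. Percent accuracy depends on response criterion and target rate as well as on discrimination, and reaction time can lengthen while d' holds or rises. If the measures disagree, the protocol does not say whether dlPFC stimulation impaired working memory. With no formal SAP planned, the protocol is the only place to settle this before the data are seen.

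There are two knock-on effects. The power statement is for one test, while the plan promises to correct over several. And Section 9.4.3 carries into the secondary correlations only those measures that show a reliable stimulation effect, so the choice of measure also shapes the tests of mechanism.

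**Working it through.** **Inputs.** From 9.2: n = 30 participants, each measured under both conditions; d = 0.53; level 0.05 (two-sided assumed, as sidedness is not stated). From 9.4.2: three N-back bullets, or 1 + 3 + 1 = 5 measures if reaction time is counted once per trial type. Assumed, because the protocol does not give them: the correlation between measures, target rate, d' level and response criterion.

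**1. The plan's own figure.** For a paired t-test the noncentrality is d√n = 0.53 × √30 = 2.903, on 29 degrees of freedom. The two-sided 0.05 critical value is 2.045, and the power is 0.801. The stated 80% is reproduced for a single test. (The 95% at d = 1.39 is not a paired figure: two independent groups of 15 give 0.957, while 30 pairs give more than 0.999. That is a separate matter and does not affect this point.)

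**2. The same effect under the promised correction.** The protocol names no method, so Bonferroni is used as an illustration.

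| Tests in the family | Level per test | Critical t | Power at d = 0.53 |
|---|---|---|---|
| 1 | 0.05 | 2.045 | 0.801 |
| 3 | 0.0167 | 2.541 | 0.642 |
| 5 | 0.01 | 2.756 | 0.564 |

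Over five measures, 80% power per measure needs d = 0.66.

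**3. Both or either.** Suppose d' and reaction time each have d = 0.53, tested at 0.05 without correction.

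- Correlation 0: both significant, 0.801² = 0.642; at least one, 1 − (1 − 0.801)² = 0.960.
- Correlation 0.7 (simulated paired t-tests, n = 30): both, about 0.71; at least one, about 0.89.

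Both are therefore significant in about 64% to 71% of trials and at least one in about 89% to 96%. The gap of roughly 18 to 32 percentage points comes entirely from a rule that the protocol does not state.

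**4. Percent accuracy at fixed d'.** Under equal-variance signal detection, with target rate p and criterion c, percent correct = p·Φ(d'/2 − c) + (1 − p)·Φ(d'/2 + c). At d' = 2 throughout:

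| Target rate | Criterion moves | Percent correct |
|---|---|---|
| 25% | 0.3 to 0 | 86.7 to 84.1 (falls) |
| 25% | 0.2 to 0 | 86.1 to 84.1 (falls) |
| 25% | 0.2 to 0.5 | 86.1 to 87.3 (rises) |
| 50% | 0.2 to 0 | 83.7 to 84.1 (rises) |

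Percent accuracy can move while discrimination does not, but the sign and size depend on quantities that the protocol does not give.

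**The case against.** Section 9.4.2 states no success rule. A reader might infer that any one significant N-back measure would count as a positive result, but the section says only that the outcomes are assessed and regressed on condition. Section 3 does supply an objective-level definition, and a result on percent accuracy or reaction time alone would not meet it. This stands, and it narrows the defect: the definition in Section 3 is not carried into the analysis.

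A reader might also infer that the trial is powered on one quantity and defined on another. Section 3 glosses accuracy as d', so the word in 9.2 may mean d' or percent correct. The protocol does not settle which, so a mismatch cannot be asserted.

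A third tempting inference is that a shift in response bias would often be reported as impaired memory. Nothing in the protocol says that cTBS moves the criterion, and step 4 shows that the effect on percent accuracy can vanish or reverse. No frequency for such an error can be given. Because d' is itself a listed outcome, and 9.4.8 promises individual values for primary outcomes, an unchanged d' would also be visible to readers.

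Finally, the count of five is one reading of three bullets. The promised correction does control chance findings. It does not say which measure decides, nor would it remove a real effect on speed or bias.

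**Conclusion.** The point holds as an inconsistency between Sections 3 and 9.4.2 that leaves the working-memory objective without a deciding measure or an any/all rule. At d = 0.53 on both d' and reaction time, the chance of a supportive result is about 64% to 71% under one rule and 89% to 96% under the other. These figures assume paired two-sided tests at 0.05 and correlations from 0 to 0.7. The 80% power in 9.2 is correct for one uncorrected test. It is about 0.64 or 0.56 per measure if Bonferroni is applied over three or five. That percent accuracy depends on the criterion is a reason not to let it decide the objective; it does not show that a false claim of impairment is likely. The matter should be corrected before the data are analysed.

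**What to change.** Align Sections 3 and 9.4.2 by naming one N-back measure that decides the objective. d' for dlPFC versus angular gyrus is the natural choice, since Section 3 lists it first and glosses accuracy as d'. State the load level at which it is taken; 9.2 powers the 2-back.

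Make percent accuracy and the reaction times supportive. Say that slowing or lower percent accuracy is read as impaired working memory only alongside lower d', and report the response criterion from the same hit and false-alarm counts. Carrying the conjunction in Section 3 into 9.4.2 would also remove the ambiguity, but it would need a single named reaction-time measure, and the joint power would be about 64% to 71% on the assumptions above.

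In 9.2, state that the 80% at d = 0.53 applies to a single uncorrected test of the deciding measure. Add that the cited effect is on accuracy and is assumed to carry over to d'.

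The cost is wording in three sections and one quantity computed from data already recorded, with no added participants or procedures. The downside is that an effect on reaction time or percent accuracy alone could no longer be claimed as the primary working-memory result.
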